## 1.0 PROTOCOL SUMMARY AND/OR SCHEMA

**Title:** Phase II study to evaluate the response to 2 induction courses (12 intravesical instillations) of Bacillus Calmette-Guérin (BCG) for high risk superficial bladder cancer

The main objective of this study is to evaluate the response rate to 2 induction courses (12 intravesical instillations) of BCG, in patients with high risk superficial bladder cancer, at 6 months after the initiation of therapy. We will enroll BCG naïve patients, as well as patients previously treated with BCG who completed therapy 12 months prior to enrollment in this study. The current standard of care for patients with high risk superficial bladder cancer is 1 induction course (6 intravesical instillations) of BCG, but this treatment course has not been effective in a randomized trial. The goal of the proposed study is to identify a more effective BCG regimen to treat high risk superficial bladder cancer.

### Study Design and Treatment plan

Patients will be treated with an induction course (6 intravesical instillations) of BCG followed by a second induction course (6 intravesical instillations), with a recovery period between the 2 treatment courses.

## 2.1 OBJECTIVES AND SCIENTIFIC AIMS

### Primary Objective

- To evaluate the response rate (by cystoscopy and cytology) to 2 induction courses (12 intravesical instillations) of BCG 6 months after the initiation of therapy.

### Secondary Objective

- To establish the proportion of patients who progress to muscle invasive disease within 6 months of initiation of a 2-induction course (12 intravesical instillations) of BCG.

### **3.1 BACKGROUND AND RATIONALE**

#### **3.2 Natural History of Bladder Cancer**

Of the more than 70,000 cases of bladder cancer diagnosed in the United States each year, approximately 70% are found to be non-muscle invasive tumors, 25% are muscle invasive, and 5% are metastatic [1]. Non-muscle invasive tumors encompass non-invasive papillary (Ta), invasive into the connective tissue (T1), and carcinoma in situ (Tis) tumors, with a 60%, 30%, and 10% occurrence, respectively. Sixty percent to 70% of these tumors will recur within 2 years, whereas 20% to 30% will progress to a higher grade or stage during the patient's lifetime [2]. High-risk non-muscle-invasive bladder disease excludes Ta low grade tumors because even though these tumors possess a high recurrence rate, they rarely progress to muscle-invasive disease. On the other hand, T1 tumors represent a heterogeneous group: some T1 tumors behave in an indolent fashion, responding to conservative therapy; others behave in a more aggressive manner and progress to muscle-invasive disease, giving them the potential to develop metastatic disease. We currently lack the ability to predict how T1 tumors will behave. What we do know is that recurrence of bladder tumors is dependent on size, site, multifocality, presence of concomitant Tis, grade, and prior history of bladder cancer [3]. At MSK, the current therapy for high-risk non-muscle-invasive tumors includes transurethral resection (TUR) followed by the instillation of BCG weekly for 6 weeks.

#### **3.3 Recurrence**

Recurrence of high-risk non-muscle-invasive bladder cancer depends on multiple factors as described above. Thirty percent to 90% of patients treated with TUR alone experience recurrence within 2 years. In a prospective longitudinal study, the National Bladder Cancer Collaborative Group A (NBCCGA) followed 133 patients treated with TUR alone and found that the following factors increased recurrence rates: tumors >5 cm, multiple tumors, grade 3 disease, concomitant Tis, T1 disease, and a positive cytologic finding [4]. The high recurrence rate observed in patients treated with TUR alone has led to the use of intravesical immunotherapy with BCG as a supplement to help decrease recurrence. Furthermore, multiple randomized trials have shown that TUR with BCG has superior recurrence-free rates, compared with TUR alone or TUR with intravesical chemotherapy [5, 6]. Thus, TUR with intravesical BCG has become the standard of care for patients with high-risk non-muscle-invasive bladder tumors and has been incorporated into multiple guidelines [3, 7]. Unfortunately, an audit of 1021 patients at MSK treated with intravesical BCG for high-risk non-muscle-invasive bladder cancer revealed that 13.7% (140/1021) of these patients did not have a response to therapy at 3 months from the start of BCG therapy. Furthermore, 20% (205/1021) and 32% (326/1021) did not have a response at 6 and 12 months, respectively. When patients without a response at 3 months were combined with patients with a recurrence at 6 months, 34% of patients experienced treatment failure at 6 months [8]. Many new treatments, such as intravesical chemotherapies and different dosing regimens of BCG, have attempted to decrease the high rate of treatment failure among patients with non-muscle-invasive bladder cancer; however, none have been successful [9].

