#### **Primary endpoint**

The study will employ a single-stage design. We are interested in the 2-induction BCG therapy if the overall response rate is  $\geq 80\%$  after the initiation of the first BCG therapy and not interested if the overall response rate is  $\leq 66\%$ . The probabilities of a type I error and type II error are set at 0.05 and 0.20, respectively. We will continue enrolling patients until 75 patients have completed their second cystoscopy on study. On completion of the trial, if  $\geq 52$  patients had a response, the regimen will be declared effective and of interest. All patients who meet the eligibility criteria for the study and enroll in it will be included in the analysis, regardless of whether they completed the full 2 BCG induction courses.

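### The 66% null appears to rest on a composite historical failure rate (34%) that does not match the trial's 6-month status endpoint; the matched historical response lies somewhere between about 66% and 80%.

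*Combined protocol and SAP*

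**What the plan says.** Section 3.3 reports an in-house audit of 1021 patients treated with BCG. It "revealed that 13.7% (140/1021) of these patients did not have a response to therapy at 3 months", and a further "20% (205/1021) and 32% (326/1021) did not have a response at 6 and 12 months, respectively". The next sentence forms a composite: "When patients without a response at 3 months were combined with patients with a recurrence at 6 months", the result was that "34% of patients experienced treatment failure at 6 months".

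The primary endpoint text in Section 14.0 sets a target response rate of at least 80% and a null of at most 66% ("and not interested if the overall response rate is" this value). It adds that "The probabilities of a type I error and type II error are set at 0.05 and 0.20, respectively". Section 4.2 repeats the two rates. Neither section derives the 66%; Section 14.0 refers to Section 3.0 for the rationale.

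Section 12.0 assesses outcome 6 months after the start of therapy. A responder has no evidence of disease in the bladder on both cytology and cystoscopy at that time.

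**The concern.** This is a single-arm trial, so the null rate takes the place of a control group. The only figure in Section 3.0 that matches a 66% null is the complement of the 34% composite. Two features of that composite raise doubt.

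First, the counts are not defined. The 205 are introduced as patients without a response at 6 months, in the same terms as the 140 at 3 months. The composite sentence then speaks of recurrence at 6 months. On the first description, the 205 could contain 3-month non-responders who still had disease. On the second, they could be only patients who had responded and then relapsed.

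Second, whichever description is right, the composite treats non-response at 3 months as failure for good. The trial does not. Section 9.1 gives the second course after the 3-month cystoscopy, Section 12.0 looks at 6-month status, and Section 13.0 makes progressive disease, not 3-month non-response, a treatment failure. A patient who is not clear at 3 months but clear at 6 is a responder in the trial and a failure in the benchmark.

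Both features push the same way, towards a null that is too low. A null set too low makes it easier to call a regimen effective when it is no better than standard treatment.

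**Working it through.** **Inputs.** From Section 3.3: 140, 205 and 326 of 1021 without a response at 3, 6 and 12 months, and the 34% composite. From Sections 4.2 and 14.0: null 66%, target 80%, alpha 0.05, power 0.80, and the sample size ("We will continue enrolling patients until 75 patients have completed their second cystoscopy on study").

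**Reproducing the 34%.**
- (140 + 205)/1021 = 345/1021 = 33.8%, which rounds to 34%. The complement is 66.2%.
- With 2 shared patients: 343/1021 = 33.6%, still 34%. With 3: 342/1021 = 33.497%, which rounds to 33%.
- So the printed 34% needs the two groups added with at most 2 patients in common.

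**Does the 12-month count show double counting?** The 12-month count, 326, is below 345. That excludes only one case, in which both figures are cumulative totals of all failures. Suppose instead that 140 patients never responded, and that 205 and then 326 are cumulative recurrences among those who did respond. Total failure is then 345/1021 = 33.8% at 6 months and (140 + 326)/1021 = 466/1021 = 45.6% at 12 months. Nothing conflicts.

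**Range of the endpoint-matched rate.** Let k be the number of the 140 who must not be added to the 205 when 6-month status is counted. They are either already among the 205, or clear at 6 months. Then

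historical response = 1 − (345 − k)/1021, with k from 0 to 140.

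The documents give no value for k. This assumes that all 205 would be scored as non-responders at 6 months.

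**Effect on the decision.** To keep this apart from the stated cut-off, I use 57 of 75. It is the smallest cut-off with exact alpha at or below 0.05 at 66% (alpha 0.041, power 0.844 at 80%). The last column is the exact binomial P(X ≥ 57) with n = 75 and the true rate equal to the historical one.

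| k | 6-month failures | Historical response | P(declared effective) |
|---|---|---|---|
| 0 | 345 | 66.2% | 0.045 |
| 35 | 310 | 69.6% | 0.141 |
| 70 | 275 | 73.1% | 0.335 |
| 105 | 240 | 76.5% | 0.602 |
| 140 | 205 | 79.9% | 0.840 |

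**Power for 75 patients if the null is reset** (smallest cut-off with exact alpha at or below 0.05, power at 80%):

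| Null | Cut-off | Alpha | Power |
|---|---|---|---|
| 66% | 57 | 0.041 | 0.844 |
| 68% | 59 | 0.029 | 0.676 |
| 70% | 60 | 0.035 | 0.569 |
| 75% | 63 | 0.043 | 0.240 |

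**The case against.** The strongest reply is that the groups are separate and 34% is right. The composite sentence uses two labels, non-response and recurrence, and combines them into a total; had the 205 already contained the 140, there would be little reason to combine. Section 3.6 names radical cystectomy as standard care after non-response to BCG, so some 3-month non-responders may have left bladder follow-up and never entered a 6-month count. The figure is also cited to a publication that the protocol does not reproduce.

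This stands as far as it goes. A reader might infer from 326 being below 345 that the audit counted patients twice. The documents do not support that, since the reading with separate groups fits every printed number. A reader might also infer that standard treatment gives an 80% response. That needs all 140 to be inside the 205 or clear at 6 months, and nothing in the documents shows it. No non-zero k in the table has direct evidence behind it.

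The reply does not remove the mismatch. Separate groups make 34% a correct composite of failure at either visit, but the trial's endpoint is status at one visit. It also leaves unexplained why the same paragraph gives 20% without a response at 6 months, the trial's own time point.

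**Conclusion.** The concern holds as a problem of definition and matching, not as proven double counting. The protocol does not say what its audit counts mean, and the benchmark it appears to use is stricter on failure than the trial's endpoint. The matched historical response is between about 66% and 80%, and the null sits at the lower end of that range. If only 35 of the 140 fall away, a cut-off with true alpha near 0.045 becomes one with a false-positive probability of 0.141. At the upper bound the null meets the target, and there is no effect left to detect.

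Two assumptions carry this: that the 66% is the complement of the 34%, which is an inference, and that the 205 count as failures at 6 months.

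The stated rule of 52 of 75 has an exact type I error of 0.317 at a true 66%. That is a separate defect and should not be charged to the audit. Correcting it alone would not settle the null.

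**What to change.** From the institution's audit data, count the distinct patients who fail the Section 12.0 definition at 6 months. State in Section 3.3 whether each count (140, 205, 326) is status at the visit, new events or a cumulative total, and how patients who left bladder follow-up or were re-treated before 6 months were handled. In Sections 4.2 and 14.0, give the source of the null, then justify or reset it and the responder cut-off by exact binomial. Restate the power for 75 patients rather than enrolling more.

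If the recount cannot be done, report the observed response rate with its exact confidence interval, show it beside the 66% to 80% historical range, and limit any claim of effectiveness accordingly. A formal test against 80% would not help, because 80% is the design's own alternative.

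The cost is a recount of an existing dataset and a protocol amendment. The downside is that the null and the stated power may become less favourable, as the second table shows. If the recount confirms 66%, the null needs only a clarifying sentence.

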### **3.4 Progression**

Progression to muscle-invasive disease or development of metastasis occurs in 20 to 30% of patients who present with non-muscle-invasive bladder cancer. The NBCCGA identified tumor grade, T1 disease, and Tis as indicators of progression. Additionally, 45% of patients with grade 3 disease experienced progression, the majority of these progressing within 24 months [4]. Herr et al. reported that 40% of patients with T1 G3 disease experienced progression [10]. Both recurrence and progression are associated with higher grade and stage of disease. Unfortunately, even with these advances in our understanding, we still cannot predict with certainty which tumors will progress. Thus, many trials are currently investigating better ways to treat and control non-muscle-invasive bladder cancer.

### **3.5 Priming of the Immune System**

BCG therapy causes a strong innate immune response, specifically via the activation of CD4+ and CD8+ T lymphocytes [11-13]. This response was shown to be the main factor responsible for eliminating tumor in a mouse model, and a correlation was demonstrated between T cell infiltration and clinical response in patients [14, 15]. *In vivo* studies using urine and blood proteomic and cytometric screens have demonstrated that several instillations of BCG are needed to produce a robust immune response [16]. More specifically, whereas the immune system is activated after the first instillation of BCG, the response is significantly amplified after the third treatment. These findings led to the hypothesis that the effects of BCG therapy are heightened after priming of the immune system. Furthermore, a recent study showed that BCG-specific immunity improved antitumor response in a mouse model of bladder cancer [16]. Mice whose bladders were primed with 3 instillations of BCG, at days 0, 7, and 14, had a more robust T cell bladder wall infiltration when compared to the control group. The authors of this study also observed BCG dissemination to regional lymph nodes and priming of IFN- $\gamma$ -producing T cells after 1 instillation of BCG and that these responses were more robust after repeated instillations. Finally, the authors demonstrated that patients with preexisting immunity to BCG, those who were PPD-positive, responded significantly better to intravesical BCG, compared with the PPD-negative control group [16]. The authors concluded that patient immunity to BCG should be assessed before initiating therapy. If patient immunity is found to be insufficient, it should be boosted via priming; this action may improve the response to BCG.

### **3.6 Rationale**

1. The standard care for patients with high-risk non-muscle-invasive bladder cancer who do not respond to BCG treatment is radical cystectomy. Surgery with radical cystectomy is associated with a complication rate of up to 60%, as well as with poor self-image owing to external urine collecting devices. There is a need for a more efficient non-surgical approach for patients with these tumors.
2. The current treatment regimen of 6 intravesical treatments with BCG is arbitrary. The proposed study will test the efficacy of a new regimen of BCG treatments.

3. The proposed study will attempt to define the acceptable clinical toxicity profile of intravesical BCG.
4. There is a need to increase the durability of the response to intravesical BCG; the treatment regimen in the proposed study will attempt to address this.
5. The proposed study will incorporate recent data that provided new insight into the T cell activity in response to BCG therapy. Furthermore, we will focus on the idea that priming the immune system will result in a more robust immunologic response against any tumor that is present.

## 4.1 OVERVIEW OF STUDY DESIGN/INTERVENTION

### 4.2 Design

[figure not shown]
The study will use a single-stage phase II design. We are interested in the 2-induction BCG therapy if the overall response rate is  $\geq 80\%$  and not interested if the overall response rate is  $\leq 66\%$ . The probabilities of a type I error and type II error are set at 0.05 and 0.20, respectively.

We will enroll/continue enrolling patients until 75 patients have completed their second cystoscopy on study. On completion of the trial, if  $\geq 52$  patients had a response, the regimen will be declared effective and of interest.

### 4.3 Intervention

**Rationale:** The current regimen of 6 intravesical instillations of BCG for high risk superficial bladder cancer is arbitrary. No randomized trials have been performed to identify the optimal number of intravesical BCG instillations needed to obtain the lowest recurrence rates.

**Treatment Plan:** Patients with high risk superficial bladder cancer will be treated with 2 induction courses (12 intravesical instillations total) of BCG. Patients will undergo a diagnostic TUR which will include a urine cytology when possible to evaluate their bladder tumor/tumors, a past TURBT and urine cytology within 60 days of treatment initiation will also suffice. If the pathological characteristics of the tumors result in the patient being deemed eligible, they will be asked to enroll in the study. A prior/current history and physical examination will also be evaluated. After the first induction course (6 intravesical instillations) of BCG, patients will be scheduled for a cystoscopy at 3 months (+/- 4 weeks). During this 3 month cystoscopy appointment patients will again submit a urine cytology prior to the procedure. If worsening tumor is found a TURBT will be scheduled at the physicians discretion. All enrolled patients will be evaluated for the primary endpoint, as defined in section 14.0, of the study, regardless of whether they received the full course of treatment.

## 5.0 THERAPEUTIC/DIAGNOSTIC AGENTS

**Agent:** BCG for Intravesical Use

**Source of supply:** TICE

**Licensing agreement:**

**Mechanism of Action:** BCG induces a granulomatous reaction at the local site of administration. The exact mechanism of action is unknown.

**Formulation, Packaging, and Storage:** BCG is supplied in a box containing 1 vial. Each vial contains 1 to  $8 \times 10^8$  CFU, which is equivalent to approximately 50 mg (wet weight), as lyophilized (freeze-dried) powder. The intact vials should be stored refrigerated, at 2° to 8°C (36° to 46°F), and should be protected from direct sunlight. The product should not be used after the expiration date printed on the label.

**Dosage Regimen and Administration:** BCG will be administered at a dose of 1 vial (50 mg) per instillation. The suspension should be prepared using aseptic technique. The administration instructions are as follows: Draw 1 mL of sterile saline (0.9% sodium chloride injection USP) at 4° to 25° into a small syringe (e.g., 3 mL) and resuspend 1 vial of BCG. Gently swirl until a homogenous suspension is obtained. Avoid forceful agitation, which may cause clumping of the mycobacteria. Dispense the cloudy BCG suspension into the top end of a catheter-tip syringe that contains 49 mL of saline diluent, bringing the total volume to 50 mL. Gently invert the syringe to mix. After the bladder has been drained, using a Foley catheter, gently instill the 50 mL mixture into the patient's bladder.

## 6.1 CRITERIA FOR SUBJECT ELIGIBILITY

- Age eligibility: 18 years and older
- Sex eligibility: Both
- Accepts healthy volunteers: No

## 6.2 Subject Inclusion Criteria

- Patients must have high risk non-muscle invasive urothelial bladder carcinoma (Tis, TaHG, or T1) that is pathologically confirmed by the Memorial Sloan Kettering Department of Pathology or a documented history of TaHG or T1 non-muscle invasive urothelial bladder tumors.
- All visible papillary lesions must be macroscopically resected within 60 days of treatment initiation.

- Absence of urothelial carcinoma involving the upper urinary tract (documented by radiological imaging or biopsy) preferably within 12 months from the start of treatment. Should the imaging or biopsy be performed outside this window it will be up to the physician's discretion to re-scan/biopsy.
- Patients who have received a single dose of mitomycin C following staging TUR.

### **6.3        Subject Exclusion Criteria**

- Currently being treated or scheduled to have radiation treatment for bladder cancer during the study.
- Treatment with intravesical BCG or chemotherapy for a patient's current <T2 tumor during the 12 months prior to the current diagnosis.
- Currently being treated or scheduled to have treatment with any systemic or intravesical chemotherapeutic agent during the study.
- Currently being treated with or having been treated in the last 12 months with any investigational drug for high risk superficial bladder cancer.
- Currently being treated for metastatic transitional cell carcinoma.
- Scheduled to have surgery for bladder cancer during the study.
- Presence of clinically significant infections or congenital or acquired immunodeficiency.

## **7.0        RECRUITMENT PLAN**

All MSK patients with a diagnosis of high risk superficial bladder cancer (TaHG, T1, Tis) who have not received any treatment within 12 months of the current diagnosis or who have a new diagnosis will be offered participation in the protocol. Both sexes and all racial and ethnic groups will be eligible to participate in this clinical trial, provided all the other eligibility criteria are met. Eligible research subjects will be identified by a member of the patient's treatment team, one of the protocol investigators, or the research team at MSK. If the investigator is a member of the treatment team, he or she will screen their patients' medical records for suitable research study participants. When a potential participant is identified, the investigator will inform the patient about this study and discuss the possibility of enrolling. Potential subjects contacted by their treating physician will be referred to the investigator/research staff of the study.

The principal investigator may also screen the medical records of patients with whom he or she does not have a treatment relationship, for the limited purpose of identifying patients who would be eligible to enroll in the study. The principal investigator would record appropriate contact information so that these patients could be approached regarding the possibility of enrolling in the study.

If a patient meets the eligibility criteria defined in section 6.0 and agrees to participate in the study, one of the Consenting Professionals listed on page 1 will conduct the Informed Consent process with the patient.

During the initial conversation between the investigator/research staff and the patient, the patient may be asked to provide certain health information that is necessary to the recruitment and enrollment process. The investigator/research staff may also review portions of the patient's MSK medical records to further assess eligibility. They will use the information provided by the patient and/or medical record to confirm that the patient is eligible and to contact the patient regarding study enrollment. If the patient turns out to be ineligible for the research study, the research staff will destroy all information collected on the patient during the initial conversation and medical records review, except for any information that must be maintained for screening log purposes.

In most cases, the initial contact with the prospective subject will be conducted by either the treatment team, investigator, or research staff working in consultation with the treatment team. The recruitment process outlined above presents no more than minimal risk to the privacy of the patients who are screened, and minimal protected health information (PHI) will be maintained as part of a screening log. For these reasons, we seek a (partial) limited waiver of authorization for the purposes of (1) reviewing medical records to identify potential research subjects and to obtain information relevant to the enrollment process; (2) conversing with patients regarding possible enrollment; (3) handling of PHI contained within those records and provided by the potential subjects; and (4) maintaining information in a screening log of patients approached (if applicable).

Patients will not be paid to participate in this study. Study participants will be responsible for some or all costs associated with the cancer treatment they receive during the study.

